**For group (B) patients the following data will be retrieved:**

- Age at diagnosis: young patients are defined as younger than 35 years.
- Surgical techniques: Preoperatively all patients will undergo physical examination of both breasts and axillae as well as bilateral mammograms and ultrasonography of both breasts. Histopathological diagnosis of cancer will be made prior to surgery. The planned procedure will be discussed. Different oncoplastic techniques will be utilized to achieve oncologically appropriate margins with either sentinel lymph node detection or axillary lymph node dissection according to the triple assessment of the patients. Surgical margins were determined by macroscopic and histologic examination of frozen sections of the breast specimens in the operating room. An adequate safety margin of 1cm was always insured. Breast remodeling will be done according to breast size, degree of ptosis and size of defect.

[figure not shown]
injle

Q

Seel

W

- Tumor characteristics: size, nodal status, presence of lympho-vascular invasion, amount of intraductal component, tumor grade, margin status, hormone receptor, and Her2 neu status.
- Margins will be regarded as negative when permanent histological examination found no ink on the tumor.
- Postoperative surgical complications will be documented if happened; seroma formation, hematoma and or wound dehiscence.
- Cosmetic outcome: The postoperative esthetic result will be evaluated asking the patients to rate the postoperative cosmetic result and their degree of satisfaction compared to the preoperative breast using a five-point scale (excellent, 5; good, 4; fair, 3; poor, 2; bad, 1). Objective assessment of the cosmetic result was done by two surgeons, rated on a visual analog scale from 1 (unacceptable result) to 10 (excellent result). Evaluation is based on 5 criteria, namely: breast symmetry, glandular tissue defects, nipple and areola reconstruction, scar quality and/or retraction, and the resultant breast shape.
- The occurrence of loco-regional recurrence or distant metastases during the follow-up period was recorded and considered as an end point for follow-up.

Three handwritten signatures are present at the bottom of the page. The first signature on the left is a stylized 'W'. The second signature in the center is a stylized 'Will'. The third signature on the right is a stylized 'H'.

## ETHICS OF RESEARCH

[figure not shown]
[figure not shown]
### Research on human or human products:

- Prospective study: Informed consent will be taken from patients. In case of incompetent patients the informed consent will be taken from the guardians.
- Retrospective study: Confidentiality of records will be considered
- DNA / genomic material: Informed consent for DNA / genomic test and for research will be taken from patients. No further tests will be carried out except with further approval of committee and patients. If the samples will travel outside Egypt the researcher will be responsible for transportation and security approval.
- All drugs used in the research are approved by the Egyptian Ministry of Health

---

### Research on animal:

- The animal species are appropriate for the test.
- After test, if the animal will suffer, it will be euthanized and properly disposed.
- After operation, it will have a proper postoperative care.

[figure not shown]
  
WJ?  
WJ  
WJ

## RESULTS

The results of this study will be assessed, tabulated and statistically analyzed in appropriate figures and tables.

int JLR

**Tailoring Surgical Management of Multifocal
Breast Cancer:is There a Possibility**

NCT03900299

Document Date: December 2, 2019

Data Management and Analysis:

The collected data was revised, coded, tabulated and introduced to a PC using Statistical package for Social Science (**IBM Corp. Released 2011. IBM SPSS Statistics for Windows, Version 20.0. Armonk, NY: IBM Corp.**). Data was presented and suitable analysis was done according to the type of data obtained for each parameter as follow :.

I-Descriptive statistics:-Frequency and percentage of qualitative variables.

II-Analytical statistics:

1. Chi-Square test was used to examine the relationship between two qualitative variables

2. Fisher's exact test: was used to examine the relationship between two qualitative variables for 2x2 tables (tables with 4 cells), when the expected count is less than 5 in more than 20% of cells

3-Monte Carlo-test was used to examine the relationship between two qualitative variables for larger than 2x2 tables (tables with more than 4 cells) when the expected count is less than 5 in more than 20% of cells

- P- value: level of significance

-P>0.05: Non significant (NS).

-P< 0.05: Significant (S).

-P<0.01: Highly significant (HS).

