**Primary objective:**

Evaluating the application of oncoplastic surgical techniques in the surgical treatment of multifocal breast cancer as regards; successful resection of tumor burden, disease control (recurrence) and cosmetic results.

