## PATIENTS

This study includes two groups of patients:

**Group (A):** All patients with operable breast cancer , admitted and managed at the Surgical Oncology unit, Alexandria Faculty of Medicine, between Jan.2010 to Dec.2015, their data are retrospectively reviewed and analyzed.

**Group (B):** All patients with operable multifocal breast cancer excluding those indicated for neoadjuvant therapy and those diagnosed as inflammatory breast cancer admitted between May.2017 to May.2018 will be offered oncoplastic breast conserving surgery and prospectively evaluated for 24 months as regards the outcomes of using different oncoplastic techniques to extend the clinical utility of BCT as a surgical management for multifocal breast cancer.

[name]

الدكتور

[name]

الدكتور

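### No Group B data cut-off is stated, and the SAP's only methods for recurrence are crude proportions, which are not a 24-month rate if follow-up is unequal

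*SAP*

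**What the plan says.** The protocol's PATIENTS section says that Group B patients are "admitted between May.2017 to May.2018 will be offered oncoplastic breast conserving surgery and prospectively evaluated for 24 months". The primary objective covers "successful resection of tumor burden, disease control (recurrence) and cosmetic results", with no time point for recurrence. The Group B methods say: "The occurrence of loco-regional recurrence or distant metastases during the follow-up period was recorded and considered as an end point for follow-up". They give no recurrence analysis and no rule for a patient seen for less than 24 months.

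Kaplan-Meier, log-rank and Cox methods do appear in the protocol, but under the Group A methods. The mention there of both groups follows a sentence on multifocal and unifocal patients, and most naturally means those two.

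The SAP is headed "Document Date: December 2, 2019" and opens "The collected data was revised, coded, tabulated and introduced to a PC using Statistical package for Social Science". It lists frequencies and percentages for qualitative variables, then chi-square, Fisher's exact and Monte Carlo tests. It contains no data cut-off or lock date, no censoring rule, no time-to-event method and no summary of follow-up. It names neither Group B nor recurrence.

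**The concern.** Two things meet here. The SAP speaks of finished data about five to six months before the last Group B patients can reach 24 months. And the only stated methods that could apply to Group B recurrence treat it as a yes/no variable. A proportion, or a contingency-table test built on it, gives an event-free patient at 18 months the same weight as one at 24 months or later.

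Recurrence is part of the primary objective, and Group B is the prospective oncoplastic group that serves it. A recurrence percentage with no time point, follow-up range or censoring would be hard to interpret or to set against other series. Readers would probably take it as a 24-month rate because the protocol states 24 months.

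**Working it through.** **Inputs from the documents.** SAP date: 2 December 2019. Group B admission: May 2017 to May 2018. Follow-up: 24 months. The days in May are not given, so 1 and 31 May bound each end of the window.

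**Assumptions not in the documents.** The SAP date is the data cut-off; time runs from admission; accrual is uniform; for the size of the error only, the hazard is constant and true 24-month recurrence is 5% (2% and 10% also tried).

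**Step 1: when 24 months is complete.** An admission on 1 to 31 May 2018 plus 24 months gives 1 to 31 May 2020. That is 151 to 181 days after 2 December 2019, or 5.0 to 5.9 months of 30.4375 days. The stated 24 months therefore cannot be reproduced for all of Group B at the SAP date.

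**Step 2: follow-up at the SAP date.** Months = (2 December 2019 − admission date) / 30.4375.
- Last patient: 550/30.4375 = 18.1 (admitted 31 May 2018) or 580/30.4375 = 19.1 (admitted 1 May 2018).
- First patient: 915/30.4375 = 30.1 (admitted 31 May 2017) or 945/30.4375 = 31.0 (admitted 1 May 2017).

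If observation stops at 24 months, the range is about 18 to 24 months. If not, it is about 18 to 31. The documents do not say which.

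**Step 3: share short of 24 months.** Everyone admitted after 2 December 2017 is short: 180 admission days if the window ends on 31 May 2018, or 150 if it ends on 1 May 2018. Share = short days / days in window. The capped mean is the mean of min(24, months) over all admission days. The uncapped mean is the midpoint of the first and last patients' follow-up.

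| Admission window | Days | Share short | Mean, capped at 24 | Mean, uncapped |
|---|---|---|---|---|
| 1 May 2017 to 31 May 2018 | 396 | 180/396 = 45.5% | 22.6 | 24.6 |
| 1 May 2017 to 1 May 2018 | 366 | 150/366 = 41.0% | 23.0 | 25.1 |
| 31 May 2017 to 31 May 2018 | 366 | 180/366 = 49.2% | 22.5 | 24.1 |
| 31 May 2017 to 1 May 2018 | 336 | 150/336 = 44.6% | 22.9 | 24.6 |

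The capped mean is 94% to 96% of 24 months.

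**Step 4: effect on a crude percentage, with the cap.** For true 24-month recurrence r, the monthly hazard is h = −ln(1 − r)/24. The expected crude proportion is the average of 1 − exp(−h × follow-up) over admission days. For r = 5%, h = −ln(0.95)/24 = 0.00214, and the crude figure is 4.72%, 4.79%, 4.70% and 4.77% for the four windows in order. For r = 10% it is 9.4% to 9.6%; for r = 2% it is about 1.9%. The relative understatement is about 4% to 6%.

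**Step 5: without the cap.** Mean follow-up is 24.1 to 25.1 months. Extra time in early patients roughly offsets the shortfall in late ones, so there need be no net understatement. The percentage is still not a rate at any defined time.

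**The case against.** The strongest reply is that a document date is not a data cut-off. Neither document says that Group B was closed on 2 December 2019. The past tense is weak evidence, because the protocol's Group B methods use it too for planned work, for example where recurrence is said to have been recorded. The SAP does not name Group B, and its sentence on collected data could describe Group A, admitted 2010 to 2015. Nor does it say that recurrence will be reported as a crude percentage. All of this stands.

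A reader might therefore infer too much: that Group B was locked early, that follow-up ran from 18 to 24 months, or that the recurrence rate is biased downward. The documents support none of these as fact. The first needs the SAP date to be the cut-off. The other two also need observation to stop at 24 months, and downward bias is not assured without that cap.

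It can also be said that the error is small. Under the assumptions used it is, although it would be larger if recurrences cluster late in the 24 months.

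What the reply does not remove is the gap itself. No cut-off is stated, and nothing in the stated methods for Group B allows for unequal follow-up, whatever the cut-off turns out to be.

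**Conclusion.** The point holds in a conditional form and should be acted on. What is certain is that Group B cannot complete 24 months before May 2020, that the SAP dated December 2019 states no Group B cut-off, and that the only listed methods that could apply to Group B recurrence ignore length of follow-up.

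What depends on the SAP date being the cut-off is that 41% to 49% of Group B (uniform accrual) would have less than 24 months, with a minimum of about 18 to 19. A description of Group B as followed for 24 months would then be untrue for nearly half the group. The numerical effect on recurrence is small: 5% shown as about 4.7% to 4.8%, given a cap at 24 months and a constant hazard. Without a cap, its direction is not established. The weight of the point lies in an undefined rate for part of the primary objective, more than in the size of any bias.

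**What to change.** State the Group B data cut-off date in the SAP, and whether observation stops at 24 months. For Group B recurrence, replace the crude percentage with the Kaplan-Meier estimate at 24 months, censoring event-free patients at last follow-up. Report it with a 95% confidence interval, the number at risk at 24 months, and the follow-up distribution (median and range). This extends to Group B a method that the protocol already specifies for Group A.

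Do not describe Group B follow-up as 24 months unless the data are locked after the last patient's 24-month date, which is 31 May 2020 at the latest.

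The cost is a little more analysis work and a slightly wider interval. Kaplan-Meier needs no delay; choosing to wait for complete follow-up would take about five to six months from the SAP date.

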## METHODS

**For group (A) patients The following data of will be included and recorded:**

- Age at diagnosis: young patients are defined as younger than 35 years.
- Surgery performed:
  - a-Breast conservation: involves lumpectomy with oncologically appropriate safety margins with either sentinel lymph node detection or axillary lymph node dissection according to the triple assessment of the patients. The introduction of different oncoplastic procedures in breast cancer surgery allows more breast conservation.
  - b-Mastectomy: modified radical mastectomy.
- Tumor characteristics: size, nodal status, presence of lympho-vascular invasion, amount of intraductal component, tumor grade, margin status, hormone receptor, and Her2 neu status(if available).
- Pathological determination of multifocal and unifocal tumors.
- The follow-up period of the patients was registered.
- The occurrence of loco-regional recurrence or distant metastases during the follow-up period was recorded and considered as an end point for follow-up.

Local recurrence is defined as recurrence in the original tumor bed (for BCS) or field of mastectomy.

Regional recurrence refers to metastatic disease in the ipsilateral axilla or supraclavicular lymph nodes or ipsilateral involvement of internal mammary nodes.

Loco-regional recurrence-free survival of patients who are pathologically multi-focal and uni-focal will be estimated using the Kaplan-Meier method and compared among different categories using log-rank tests (univariable analysis

in 4/12

([name])

of risk factors for loco-regional recurrence among multi-focal and uni-focal breast cancer patients).

Distal recurrence-free survival for both groups will be analyzed using the same test (univariable analysis of risk factors for distal recurrence).

Associations with local recurrence in uni-focal and multi-focal breast cancer patients are further evaluated using multivariable Cox proportional hazards regression model and summarized with hazard ratios 95 % confidence intervals (CIs).

Associations with distal recurrence uni-focal and multi-focal breast cancer patients will be further evaluated using multivariable Cox regression model.

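### For the Group B outcomes behind the primary objective, the SAP gives no confidence interval for the clear-margin or recurrence rate, and no method for recurrence if follow-up is incomplete

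*SAP*

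**What the plan says.** The protocol's primary objective concerns oncoplastic surgery for multifocal disease and names three outcomes: resection success, recurrence and cosmetic result. It does not name a group. The Patients section makes the link: Group B is the prospective cohort offered oncoplastic conservation, admitted May 2017 to May 2018 and evaluated for 24 months.

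The Group B part of Methods defines the outcomes but gives no analysis for them:
- Margins: "Margins will be regarded as negative when permanent histological examination found no ink on the tumor".
- Recurrence: "The occurrence of loco-regional recurrence or distant metastases during the follow-up period was recorded and considered as an end point for follow-up".
- Cosmesis: a five-point patient rating, and an assessment by two surgeons, "rated on a visual analog scale from 1 (unacceptable result) to 10 (excellent result"), based on five criteria.

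The SAP says that analysis followed the type of data and then lists the methods. For description it has "Frequency and percentage of qualitative variables". For analysis it has chi-square, Fisher's exact and Monte Carlo tests, all for two qualitative variables.

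Time-to-event methods do appear in the protocol, but under the heading "For group (A) patients The following data of will be included and recorded". There, loco-regional recurrence-free survival in multifocal and unifocal patients "will be estimated using the Kaplan-Meier method and compared among different categories using log-rank tests". The only 95% confidence intervals in either document are those for the Cox hazard ratios in the same section.

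**The concern.** With no comparator in Group B, the primary results are rates, and a rate from roughly one year of admissions at one unit needs a statement of precision. A bare percentage does not show how low the true clear-margin rate, or how high the true recurrence rate, could be. The study also aims to produce recommendations for managing multifocal disease, so a reported zero or near-zero recurrence rate could be given more weight than the data can bear.

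The two rates differ in what a reader can repair. An exact interval for margins can be rebuilt from the count and the denominator. A 24-month recurrence estimate under incomplete follow-up cannot be rebuilt without individual follow-up times, because a simple percentage counts a patient who was lost or cut off early as recurrence-free.

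**Working it through.** The documents state no sample size, event count, target rate or precision, so there is no figure of the plan's own to reproduce. The sizes and rates below are assumptions.

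**1. Precision of the two rates.** Inputs: assumed n = 20, 30, 50; exact (Clopper-Pearson) 95% limits from beta quantiles. For zero events the upper limit is 1 − 0.025^(1/n).

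| n | 0 recurrences: upper limit | 1 recurrence: upper limit | 90% clear margins: 95% CI |
|---|---|---|---|
| 20 | 16.8% | 24.9% | 18/20: 68.3-98.8% |
| 30 | 11.6% | 17.2% | 27/30: 73.5-97.9% |
| 50 | 7.1% | 10.6% | 45/50: 78.2-96.7% |

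If the true 24-month risk were 10%, 20 fully followed patients would show no recurrence with probability 0.9^20 = 12.2%.

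**2. Could follow-up be incomplete?** From the documents: accrual May 2017 to May 2018, 24 months of evaluation, SAP dated December 2, 2019. A patient admitted in May 2018 reaches 24 months in May 2020. No data cut is stated. Assume a cut on the SAP date and uniform accrual. Patients admitted after December 2, 2017 would then have under 24 months. Their share depends on which May dates are used:
- May 1 to May 1: 150/365 = 41.1%
- May 31 to May 1: 150/335 = 44.8%
- May 1 to May 31: 180/395 = 45.6%
- May 31 to May 31: 180/365 = 49.3%

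Follow-up would run from about 18.1 to 31.0 months.

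**3. How much would a crude percentage be off?** Assume a true 24-month risk of 10% with constant hazard λ = −ln(0.9)/24 = 0.00439 per month. Losses are exponential with rate μ, zero or set to lose 20% or 30% by 24 months. For potential follow-up u, the expected crude proportion is λ/(λ+μ) × (1 − exp(−(λ+μ)u)), averaged over the follow-up range in step 2.

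| Lost by 24 months | Capped at 24 months | All follow-up counted |
|---|---|---|
| 0% | 9.4-9.6% | 10.0-10.4% |
| 20% | 8.5-8.7% | 9.0-9.3% |
| 30% | 8.0-8.2% | 8.4-8.7% |

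The crude figure is therefore at most about 2 points below 10% (10.0 − 8.0), and is not understated at all if there are no losses and all follow-up is counted. At n = 20 the interval around zero events spans 16.8 points. Imprecision is much the larger issue.

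**4. Zero events.** A Kaplan-Meier interval has zero width when there are no events. The exact upper limit for the expected number of events is −ln(0.025) = 3.689. With mean follow-up m capped at 24 months (22.5 to 23.0 months in step 2, no losses), the implied 24-month upper limit is 1 − exp(−24 × 3.689/(n × m)): 17.5-17.8% at n = 20, 12.1-12.3% at n = 30 and 7.4-7.6% at n = 50. This conversion assumes a constant hazard.

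**5. Does the Group A text reach Group B?** One sentence there reads "Distal recurrence-free survival for both groups will be analyzed using the same test". It follows a sentence about multifocal and unifocal patients and most naturally means those. Even read as Groups A and B, it covers distal recurrence only and states no interval.

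**The case against.** The best defence is that each part is modest. A percentage is the right summary for a one-time binary margin result, and its interval can be rebuilt from the counts. For recurrence, the protocol sets 24 months of evaluation for every Group B patient; if that is achieved, a 24-month proportion is valid and an exact binomial interval is all it lacks. These points stand, and they make any survival method conditional on incomplete follow-up.

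Three stronger readings are tempting and are not supported:
- *That the planned recurrence percentage is seriously biased.* Neither document gives a data cut. The SAP date is only a document date, and the 41-49% share, the loss rates and uniform accrual are all assumed. Even then the understatement is small.
- *That recurrence must be analysed as a time-to-event outcome.* Making recurrence the end of follow-up says when observation stops. It does not rule out a proportion at a fixed 24 months.
- *That the surgeon score cannot be analysed at all.* Whole-number ratings from 1 to 10 could be tabulated like the five-point patient rating, which the SAP's frequencies do cover. What is missing is a numeric summary and a statement of how two raters and five criteria are combined. This is minor.

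A further caution concerns the remedy. Because either type of recurrence ends follow-up, separate Kaplan-Meier curves for loco-regional and distant recurrence would let each event censor the other and would slightly overstate each cumulative incidence. With assumed 24-month risks of 5% and 10%, the figure for the first would be 5.0% against a cumulative incidence of about 4.75%.

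**Conclusion.** The concern holds for the SAP's treatment of Group B. For estimation the SAP supplies frequencies and percentages only. It gives no interval for the margin-negative or recurrence rate and no rule for recurrence if follow-up is incomplete, and the Group B part of the protocol does not fill the gap. The missing interval carries the weight of the point; the size of that gap rests on the assumed 20 to 50 patients. The follow-up part is secondary, since it depends on an early data cut or on losses that the documents do not report. This is an inexpensive improvement to the plan. It does not show that the results would be wrong.

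**What to change.** Add the following to the SAP, labelled as specified after December 2, 2019:

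1. Report the Group B margin-negative rate with count, denominator and exact (Clopper-Pearson) 95% CI.
2. If every patient has 24 months of follow-up, report 24-month recurrence as a proportion with an exact 95% CI. Otherwise report a 24-month Kaplan-Meier estimate of first recurrence, loco-regional and distant combined, with 95% CI and the number at risk at 24 months. Give the two types separately as cumulative incidence, with the other type and death as competing events. If there are no events, give the exact person-time upper limit and state the constant-hazard assumption.
3. Minor: summarise the 1-10 surgeon score by median and interquartile range, stating whether this is per rater, the mean of the two raters, or per criterion.

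The cost is a little more analysis work, using the surgeon scores already planned and the dates of surgery, recurrence, death and last follow-up. Results will look less certain than a bare percentage, and a Kaplan-Meier estimate at 24 months would rest on few patients at risk if data were cut early.

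### The SAP names no method that uses the order of the five-point cosmetic rating or of tumor grade; its table tests are valid but less efficient for one-directional effects

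*SAP*

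**What the plan says.** The SAP is one short section. Its descriptive part is "Frequency and percentage of qualitative variables". Its analytical part has three items:

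- The default: "Chi-Square test was used to examine the relationship between two qualitative variables".
- Fisher's exact test, which "was used to examine the relationship between two qualitative variables for 2x2 tables (tables with 4 cells"), when expected counts are low.
- For sparse larger tables: "Monte Carlo-test was used to examine the relationship between two qualitative variables for larger than 2x2 tables". The statistic behind this test is not named.

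The significance rule is "P< 0.05: Significant (S"), with no statement on sidedness. The SAP mentions neither the cosmetic rating nor grade by name.

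The protocol's primary objective includes cosmetic results. In Methods for group (B), patients rate the result on a "five-point scale (excellent, 5; good, 4; fair, 3; poor, 2; bad, 1"). Two surgeons also score it, "rated on a visual analog scale from 1 (unacceptable result) to 10 (excellent result"). Tumor grade is recorded in both groups. Secondary objectives 2 and 3 concern the use of mastectomy and the factors associated with breast-conserving therapy (BCT). For group (A), the protocol separately plans log-rank tests and multivariable Cox models for recurrence.

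**The concern.** A Pearson Chi-square statistic is unchanged if the columns of the table are rearranged, and so is a Monte Carlo P value based on it. Such a test treats bad, poor, fair, good and excellent as five unrelated labels. Against a two-level factor it spends 4 degrees of freedom, although the natural question (do ratings tend to be higher in one subgroup?) needs 1. The same applies, less strongly, to grade against operation type.

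At stake is the chance of seeing a real difference in cosmesis between patient or operation subgroups, or a real gradient in the use of BCT by grade. The listed tests also give no effect estimate with a confidence interval. The planned percentages show direction and descriptive size, but not precision.

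**Working it through.** The documents give no sample size, power or effect size for these comparisons, so there is no stated figure to reproduce. The check asks what ignoring order costs.

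**Inputs from the documents.** Significance at 0.05 (SAP; two-sided assumed). Five levels for the rating (protocol, Methods, group (B)).

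**Assumptions.** Three levels for grade (number not stated). Comparison of two subgroups, giving 4 df (rating) or 2 df (grade) for the unordered test and 1 df for the ordered test.

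**Step 1: analytic comparison.** Suppose the whole departure from the null lies along the ordering, so that both tests have the same noncentrality λ.

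- Choose λ so that P(χ²₁(λ) > 3.841) equals the target power. For 80%, λ = 7.849; for 90%, λ = 10.507.
- Unordered power at the same λ is P(χ²₂(λ) > 5.991) for three levels and P(χ²₄(λ) > 9.488) for five.
- λ is proportional to sample size, so the extra patients needed follow from the ratio of the λ values that give equal power.

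| Levels | Ordered power | Unordered power | λ needed by unordered test | Ratio |
|---|---|---|---|---|
| 5 | 80% | 59.5% | 11.935 | 11.935/7.849 = 1.52 |
| 5 | 90% | 74.0% | 15.405 | 15.405/10.507 = 1.47 |
| 3 | 80% | 70.9% | 9.635 | 9.635/7.849 = 1.23 |
| 3 | 90% | 83.5% | 12.654 | 12.654/10.507 = 1.20 |

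At 80% power the loss is 80 − 59.5 = 20.5 points on five levels and 80 − 70.9 = 9.1 points on three.

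**Step 2: illustrative simulation.** 1,500 tables per setting and 999 Monte Carlo draws with fixed margins, comparing the Pearson statistic with a Wilcoxon midrank statistic. Assumed reference distributions: 5/10/20/35/30% from bad to excellent, and 10/55/35% for three levels. The second subgroup is shifted by a proportional-odds odds ratio (OR). Entries are unordered vs ordered power, in percent.

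| Per subgroup | 5 levels, OR 2.5 | 5 levels, OR 3.5 | 3 levels, OR 2.5 | 3 levels, OR 3.5 |
|---|---|---|---|---|
| 15 | 16.7 vs 26.3 | 27.3 vs 41.3 | 14.3 vs 16.7 | 27.1 vs 31.9 |
| 20 | 20.5 vs 31.8 | 37.3 vs 53.7 | 21.7 vs 27.2 | 38.1 vs 44.8 |
| 30 | 31.5 vs 44.9 | 53.3 vs 70.5 | 32.7 vs 38.3 | 55.3 vs 62.3 |
| 50 | 48.7 vs 70.7 | 78.2 vs 91.0 | 51.5 vs 60.4 | 80.3 vs 86.7 |

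The loss is about 10 to 22 points on five levels and about 2 to 9 on three.

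**Step 3: validity.** With OR 1, rejection rates across both tests were 4.3% to 5.3% on five levels and 3.5% to 5.3% on three. Neither test is invalid.

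**Step 4: non-monotone pattern.** With 30 per subgroup and a second subgroup at 15/5/5/25/50%, unordered power was 53.6% vs 20.5% ordered. On three levels, with 30/15/55%, it was 87.9% vs 7.1%. The advantage reverses.

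**The case against.** The strongest reply is that the criticized comparison is not in the documents. The SAP speaks generically of qualitative variables and says that "suitable analysis was done according to the type of data obtained for each parameter". Group (B) is a single arm, and frequencies and percentages may be enough to describe its cosmetic results. Any two-subgroup table of ratings is therefore a construction, and its size is unknown. This stands, and it is why the simulated figures are only illustrative. It does not remove the point: the clause about data type leads to a list in which no entry uses order.

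A reader might infer several stronger conclusions that the documents do not support:

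- *That ordered variables are tested only by unordered tests.* The SAP assigns neither variable to a test, and the Monte Carlo statistic is unnamed, so unordered is the likely reading rather than a stated one. The protocol's log-rank and Cox analyses of recurrence in group (A) are separate, and grade may enter them. They do not cover the choice of operation.
- *That a large share of power is lost for both variables.* This fits the five-level rating. For a three-level grade the loss is moderate.
- *That small samples make the loss serious throughout.* No sample size is given. A small group (B) is a reasonable inference from one year's intake at one unit, but the protocol describes the retrospective series as large, and that is where grade against operation type would mainly be examined.
- *That the planned P values are wrong.* They are valid; the issue is efficiency.

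The dependence on a monotone effect also stands. A one-directional shift is the natural question for a scale from bad to excellent, but it is not guaranteed for every factor.

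**Conclusion.** The point holds as one of efficiency and reporting. For associations with another categorical variable, including those under objectives 2 and 3, the SAP lists only tests that appear to ignore order. For a one-directional effect that an ordered test would detect with 80% power, the cost is about 20 points on the five-level rating and about 9 points on a three-level grade. Matching that power would take about 52% and 23% more patients respectively.

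The analytic figures rest on a two-sided 0.05 level, two subgroups, an effect that lies wholly along the ordering and, for grade, three levels. The simulated figures also rest on assumed distributions, odds ratios and subgroup sizes. The change is worth making because the rating belongs to the primary objective and the cost is almost nil.

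**What to change.** Amend the analytical section of the SAP as follows:

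1. State which subgroups, if any, will be compared on the five-point rating. Use Mann-Whitney (two subgroups) or Kruskal-Wallis (more than two).
2. For grade against operation type, use a linear-by-linear (Cochran-Armitage) trend test.
3. Use exact or Monte Carlo P values for these ordered tests when tables are sparse.
4. Report a proportional-odds odds ratio with 95% CI beside the P value.
5. Keep Chi-square, Fisher's exact and the Monte Carlo test for unordered variables, and name the statistic behind the Monte Carlo test.

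The cost is SAP wording and standard software procedures, with no new data. The small downside is lower power for non-monotone patterns; the percentages already planned would help to show these. The SAP is dated December 2019 and written in the past tense. If the analysis has already been run, add the ordered tests beside the reported ones and label them post hoc.
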